**Project Title:**

Safety, Feasibility, and Impact of Preoperative Respiratory Strength Training in Cardiac Surgical Patients

**Abstract:**

The prevalence of postoperative dysphagia (swallowing impairment) is critically high in patients with cardiovascular disease who undergo cardiac surgery (CS) with estimates ranging from 3%-94%. Notably, postoperative dysphagia in CS patients has been linked to morbidity and mortality. A recent research study that prospectively examined postoperative dysphagia in a cohort of 182 CS patients revealed that CS patients who aspirated but had an effective cough response had reduced rates of pneumonia, intubation, death, and hospital readmission, and also had a shorter hospital length of stay (LOS)/reduced health care costs. These findings indicate that an effective cough response may lead to improved health-related outcomes in CS patients, implying that therapeutics focused on improving cough peak expiratory flow rate may be beneficial. Respiratory strength training (RST) is a treatment approach that has led to improvements in cough strength and effectiveness in a variety of patient populations with dysphagia. Given its effectiveness in improving pulmonary and swallow function in high-risk patients with dysphagia, implementing RST preoperatively may be an effective approach to prevent postoperative impairments in airway clearance physiologic capacity and swallowing, thereby mitigating postoperative adverse health-related outcomes. Therefore, this pilot research study will investigate the safety, feasibility, and impact of a preoperative RST program in CS patients with reduced airway clearance physiologic capacity via three specific aims: 1) Determine the safety and feasibility of a preoperative RST program; 2) Examine the impact of a preoperative RST program on expiratory, inspiratory, and airway clearance physiologic capacity; and 3) Investigate the impact of a preoperative RST program on swallowing safety and health-related outcomes in CS patients. To determine the safety and feasibility of RST, attendance at telehealth/in-person sessions, RST adherence, and adverse outcomes will be tracked. To examine the impact of RST on patient outcomes, longitudinal evaluations of breathing and swallowing will be performed, and health-related outcomes tracked. This is the first study to explore preoperative RST in CS patients to improve swallowing safety and mitigate adverse health-related outcomes. Findings will provide preliminary data to support clinical utility of preoperative RST in high-risk CS patients and will support further research in a larger cohort of CS patients to elucidate the efficacy of RST and to determine the optimal training regimen and patients who would benefit from RST.

**SPECIFIC AIMS:**

We seek to examine the safety, feasibility, and clinical utility of a preoperative respiratory strength training (RST) program in cardiac surgical (CS) patients with the following specific aims:

**Aim 1: Test the hypothesis that a preoperative RST program will be safe and feasible in CS patients.** *Approach:* CS patients will complete at-home RST with weekly telehealth sessions and one in-person session at mid-point. Attendance, RST adherence, and adverse events will be tracked.

**Aim2: Test the hypothesis that a preoperative RST program will improve respiratory and airway clearance physiologic capacity in CS patients.** *Approach:* Forced vital capacity, maximum expiratory and inspiratory pressure, voluntary cough peak expiratory flow, and cough spiroometry metrics will be obtained before and immediately after RST. Functional measures of dyspnea and speech rate/pausing during speech will also be tracked (London Chest Activity of Daily Living scale [LCADL], Bamboo passage). Descriptive statistics and a repeated measures analysis will evaluate potential change in physiologic metrics of interest.

**Aim 3: Test the hypothesis that a preoperative RST program will improve postoperative respiratory, swallowing and health-related outcomes.** *Approach:* Following surgery, a fiberoptic endoscopic evaluation of swallowing will be performed and health-related outcomes examined.

Outcomes will provide needed ‘proof of concept’ feasibility and safety data and deliver preliminary insights into the potential role of a *proactive, targeted, and mechanistically guided* ‘prehabilitation’ for CS patients to improve airway clearance capacity and health-related outcomes. If hypotheses are confirmed, these data will support future large-scale clinical trials.

#### SIGNIFICANCE:

A reported 30.3 million Americans, or 12.1% of the population, are living with cardiovascular disease (CVD), conferring an annual economic cost of ~\$219 billion. According to the American Heart Association, more than 1 million adults undergo cardiac surgical (CS) procedures in the United States annually, with this number expected to increase over the next decade. Unfortunately, swallowing difficulty (dysphagia) is a common postoperative complication of CS that is associated with poor patient outcomes. We recently conducted the first prospective study utilizing instrumental imaging techniques and validated swallowing outcomes in CS patients. In the 182 CS patients examined with fiberoptic endoscopic evaluation of swallowing (FEES), unsafe swallowing was confirmed in 94% of patients (66% penetration, 29% aspiration) and inefficient swallowing (pharyngeal residue) in 52% (Fig. 1) following extubation. Of significance was our findings that postoperative aspiration was associated with an 85-hour delay to resume oral intake, a 43% increased length of hospital stay, ~\$50,000 increased cost of care, pneumonia (OR: 2.6), reintubation (OR: 5.7), and death (OR: 2.8). Swallowing profiles, aspiration risk factors, and associated outcomes from this study are summarized in Figure 1.

[figure not shown]

Fig. 1: Prevalence, risk factors and outcomes of dysphagia in 182 CS postoperative patients.

Closer inspection of these data revealed significant differences in health-related outcomes among aspirating CS patients when stratified by cough response profiles. Specifically, aspirators who produced an effective cough to expel tracheal aspirate from the airway demonstrated significantly reduced rates of pneumonia, reintubation, mortality, readmission, LOS, and cost of care compared to aspirators who could not eject tracheal aspirate from the airway (Table 1). Thus, a **CS patient’s physiologic capacity to produce a strong and effective cough was a significant prognostic factor** in aspirating individuals. Given that **cough strength represents a modifiable physiologic variable**, this finding was of high clinical significance, *revealing a potential treatment target to improve CS patient outcomes that motivate this proposal.*

**Table 1. CS patient outcomes stratified by cough response profiles to expel tracheal aspirate.**

[figure not shown]
Outcome: N (%)	CS Aspirators with:		CS Non- Aspirators:	P Value:
	Absent / Ineffective Cough	Effective Cough:		
Pneumonia	10/44 (23%)	0/8 (0%)	11/130 (9%)	0.04*
Reintubation	13/45 (29%)	0/8 (0%)	7/130 (5%)	<0.001*
90-day Mortality	4/44 (9%)	0/8 (0%)	1/130 (1%)	0.04*
30-day Readmission	4/26 (15%)	0/5 (0%)	13/85 (15%)	0.33

Our data, combined with other published reports documenting suboptimal outcomes in aspirating CS patients, highlight the *need for targeted interventions to improve swallowing and airway clearance abilities in CS patients that mitigate the development of associated sequelae and improve patient outcomes*. Unfortunately, no such intervention studies currently exist in the literature, resulting in gaps in knowledge and suboptimal patient care in this area.

While many dysphagia risk factors cannot be modified, **airway physiologic capacity represents one dysphagic risk factor that can be modified (increased) via targeted exercise programs**. Respiratory strength training (RST) has been utilized across several high-risk dysphagia patient populations that is noted to improve physiologic and patient outcomes. First applied in individuals with Parkinson's disease (PD), a 4-week RST was noted to increase cough effectiveness, swallowing safety (penetration-aspiration scale [PAS] scores), and hyolaryngeal excursion during swallowing. Likewise, a 4-5 week RST program implemented in stroke survivors was reported to improve maximum expiratory pressure (MEP), cough peak expiratory flow, cough volume acceleration, reflexive urge to cough responses, and swallowing safety. Similarly, in HNC patients with chronic radiation associated dysphagia, implementation of an 8-week RST program led to improved expiratory pressure generating capacity, swallowing safety, and patient reported quality of life.

**Fig. 2: RST improves physiologic capacity in a**

To date, **no group has examined the impact of a combined inspiratory and expiratory RST program in CS patients** targeting increased upper airway physiologic capacity before surgery that may impact postoperative patient outcomes. Here, we seek to inform current knowledge gaps by examining the utility of a proactive, preoperative RST program in a small cohort of CS patients. Our central supposition is that a preoperative RST program will improve a CS patient's physiologic capacity to defend the airway and thereby improve CS postoperative patient outcomes.

## APPROACH:

**Overview:** The current *pilot* project seeks to determine the safety, feasibility, and impact of preoperative RST program in 25 CS patients who are at high risk for developing post-surgical dysphagia. Thus, this represents a 'proof of concept' study to support subsequent larger-scale clinical trials. Briefly, *Aim 1* will examine the feasibility and safety of the RST program by monitoring treatment adherence, telehealth/in-person session attendance, and closely monitoring adverse events related to RST. *Aim 2* will determine the physiologic impact of the RST program by comparing measurements of forced vital capacity (FVC), MEP, MIP, voluntary cough peak expiratory flow (PEF), and cough spirometry metrics as well as functional measures of dyspnea and (LCADL, Bamboo passage), before versus after RST (i.e., research exam 1 vs. research exam 2, Fig 3). Additionally, a FEES will be performed to index baseline swallowing and to provide secondary treatment outcomes indexed by the validated penetration-aspiration scale (PAS), dynamic imaging grade of swallowing toxicity (DIGEST), the New Zealand secretion scale (NZSS), and the Yale pharyngeal residue severity rating scale (YRS). Completion of Aims 1 and 2 will occur within one month prior to surgery (Fig. 3). *Aim 3* will involve monitoring and collection of health-related outcomes during the postoperative recovery phase and postoperative pulmonary function testing and FEES following extubation. This study timeline is depicted in Figure 3.

[figure not shown]

Fig. 3: Study Timeline.

**Design:** This study represents a *longitudinal pilot cohort study* intended to collect preliminary data regarding the safety and feasibility of a preoperative intervention program, to inform larger comparative studies that will utilize a between groups comparison. Similar study designs have been implemented in other pilot treatment studies in speech-language pathology. While study designs involving group comparisons were considered for this project, the current design was chosen to ensure feasibility and a tightly conducted pilot or proof of concept study to allow detailed and rigorous outcomes and analyses. Further, consideration was given to the nature, scope, budget, and timeline of this grant mechanism intended for new investigators, and it was determined that a smaller, feasible study was most appropriate.

**Participants:** Twenty-five individuals undergoing cardiovascular surgery will be enrolled in this pilot project. Eligibility requirements are:

### Inclusion criteria:

1. Adult 18-90 years old.
2. Not pregnant.
3. Undergoing planned cardiac surgery via sternotomy &/or extended thoracotomy & seen in the UF Health preoperative clinic.
4. Confirmed COVID-19 negative test and/or no recent COVID-19 symptoms
5. Has access to a computer, tablet, or electronic device with a stable internet connection for telehealth sessions.
6. Willing to undergo testing procedures and complete the exercise training program

### Exclusion Criteria:

1. Individuals under the age of 18 or over the age of 90.
2. Pregnant women.
3. Positive for COVID-19 or symptoms of COVID-19.
4. No access to a computer, tablet, or electronic device &/ a stable internet connection for telehealth sessions.
5. Unwilling to undergo testing procedures and/or complete the exercise training program.

**Recruitment:** [name] is a faculty member of the Department of Surgery, Division of Cardiovascular Surgery, and therefore has close ties with this patient population and clinical setting. Further, the ARC Lab has a strong history of successful collaborations with the cardiothoracic surgeons at the UF Heart and Vascular hospital (Drs. [name], [name], [name], [name]) who see patients in this preoperative clinic. Participants will be recruited from the preoperative clinic visit. Drs. [name] and [name] will identify eligible participants who meet inclusion criteria from clinic schedules and will approach identified individuals who will be informed of their potential eligibility to participate and asked if they would like to learn about this study. If they express interest, an approved study team member listed on this protocol will verbally detail the aims of the study, specific requirements for inclusion, and answer any questions from patients and caregivers. They will also be provided with a copy of the informed consent form to read over. Those who wish to be enrolled will sign an informed consent form, will be provided a copy of the signed informed consent form, assigned a subject identifier, and an appointment will be scheduled for their Research Evaluation 1.

**Research Evaluations:** CS patients will undergo three separate research examinations during this study. Before commencing the RST program, an initial research examination (pulmonary function testing, functional speech/dyspnea measures) will be completed. After completing RST and before undergoing surgery, a second research examination (pulmonary function testing, FEES, functional speech/dyspnea measures) will be completed. Finally, postoperatively, a third research examination (FEES) will be completed. The methods for the research examinations are outlined in detail below.

**Research Evaluation 1:** As previously described, CS patients will undergo evaluations during the preoperative phase immediately before and after the RST program. Research evaluations will take approximately 30-45 minutes to complete. During these evaluations, the following procedures and outcomes will be collected:

**Pulmonary function testing (PFT):** Consistent with PFT protocols and the American Thoracic Society guidelines, all PFT measures will be completed in an upright seated position with a nose clip. FVC will be measured with a handheld spirometer (Micro I; Carefusion, Yorba Linda, California). For FVC, CS patients will be instructed to take a deep breath in, place their mouth around the mouthpiece, and blow all the air out from their lungs. MEP and MIP will be measured with the MicroRPM handheld MEP device (Micro Direct Inc., Lewiston, ME). For MEP testing, CS patients will be instructed to place their mouth around the mouthpiece and blow out as forcefully as possible. For MIP testing, CS patients will be instructed to place their mouths around the mouthpiece and breathe in as forcefully as possible. The participant will perform up to three trials of each task, inter-spaced with a one-minute rest in between. The highest value will be used for statistical analysis. Voluntary cough PEF will be tested using a handheld analog Mini-Wright Peak Cough Flow Meter (model number 3103085, Clement Clarke Int., Harlow, United Kingdom). This device is considered the gold standard Peak Cough Flow (PCF) device and is one of the only PCF devices that contains a one-way expiratory valve that prevents a participant to breathe air in from the device to reduce contamination. Additionally, we will fit the PCF meter with a Mini-Wright disposable single-use bacterial expiratory one-way valve filter mouthpiece (model number 3122064) that traps any expectorated matter or organisms ensuring a barrier to the PCF meter device. This method conforms to the American Thoracic Society (ATS) standards for PCF testing. Participants will be instructed to "cough hard like something is stuck in your throat." The participant will perform three trials inter-spaced with a one-minute rest in between. The outcome will be **Peak Expiratory Flow** ((PEF) L/min). The highest obtained value will be used. For cough spirometry testing, an oral pneumotachograph (MLT 1000; ADInstruments, Inc., Colorado Springs, Colorado) will be connected to a spirometry mouthpiece filter (MQ 304 Spirometer Filter; Vacumed; Ventura, California). Participants will be instructed to wrap their lips around the mouthpiece and "cough hard like something is stuck in your throat." Cough waveforms will be recorded using LabChart Version 7 (Microsoft Corp., Redmond, Washington) and a laptop computer devoted to this study. Cough spirometry metrics will include inspiratory phase duration, inspiratory peak flow rate, compression phase duration, expiratory rise time, peak expiratory flow rate, and cough volume acceleration. Up to three attempts will be elicited. An example of voluntary cough spirometry waveform from a previous study in our lab is provided in Fig. 5 and definitions for each outcome of interest is provided in Table 3 below.

**Table 3. Definitions of cough spirometry outcomes of interest**

Cough Outcome:	Definition:
Inspiratory phase duration (s)	Time from onset of inspiration at 0L/s to the beginning of glottic closure or the start of the expiration onset
Inspiratory peak flow rate (L)	Peak inspiratory flow during the inspiratory phase
Compression phase duration (s)	Time to glottic opening; end of the inspiratory phase to the start of the expiratory phase
Expiratory rise time (s)	Time from the expiration phase to the peak of the expiratory flow
Peak expiratory flow rate (L)	Peak expiratory airflow during the expiratory phase of cough
Cough volume acceleration (L/s/s)	Peak expiratory flow rate /expiratory rise time

Note: L=liters, s=seconds

**Functional Dyspnea Measure:** Research participants will complete the London Chest Activity of Daily Living scale (LCADL), which is a standardized and validated 15-item questionnaire that measures dyspnea during activities of daily living.

**Speech Measure:** The 'Bamboo Passage' is a validated speech testing item that consists of a 98-word paragraph. It is used to determine speaking rate, and number and duration of pauses during speech. Participants will be instructed to read the passage in their normal speaking rate and loudness. Speaking rate (words per minute), number of pauses, and duration of pauses will be calculated.

A digital audio recorder (TASCAM, DR40) connected to a condenser headset microphone (AKG, Inc., HSC271) with a lapel windscreens (eBoot, Inc.) will be placed on the participants head with the headset microphone at a standardized distance of 10cm from the right lip corner. Audio recordings will be digitized at 44.1 kHz with a 16-bit quantization. Calibration of the microphone will be completed prior to each test. Speech testing items will be recorded and saved for subsequent offline analysis. Audio recordings obtained during speech testing will be blinded and rated in Audacity (Audacity 2.2.2, WordPress, 2018) for the below speech outcomes.

**Aim 2 Outcomes:** Given our desire to index physiologic capacity, we will utilize the highest obtained outcome for FVC, MEP, MIP, cough PEF, and cough spirometry metrics at each time point before and after RST for statistical comparisons. LCADL ratings and speech measurements will also be compared before and after RST. We hypothesize that CS patients will improve FVC, MEP, MIP, cough PEF, cough spirometry metrics, dyspnea, and speaking rate/pauses post-RST.

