The RST protocol will be the previously utilized “Rule of 5’s” that includes training 5 days per week and performing 5 sets of 5 reps (i.e., 25 repetitions) for both expiratory and inspiratory muscle strength training. Thus, a total of 50 repetitions (25 IMST, 25 EMST) will be performed by enrolled participants. CS patients will be instructed to breathe in (IMST) or out (EMST) for several seconds until the valve audibly releases. Between repetitions, CS patients will be instructed to rest 10-15 seconds before the next repetition. After each set, CS patients will be instructed to rest for one minute before completing the next set. Repetitions will be recorded in a training log provided to the CS patients to track adherence and the quality of repetitions will be monitored during weekly telehealth sessions.

Telehealth Sessions: CS patients will complete one-five training sessions per week via telehealth with a research speech-language pathologist to ensure patients are using correct form and technique, to complete a safety and adverse event check, to answer any questions patients may have, and to assist with adherence issues. The number of telehealth visits per week will be determined based on individual patient factors including 1) patient performance of the RST program, and 2) patient requests for additional training/clarification. The research speech-language pathologist may recommend up to 5 telehealth visits per week and/or patients may request additional telehealth sessions (up to 5 per week) if they have questions or require additional support to perform the RST exercises correctly. EMST/IMST devices will also be recalibrated weekly using the Borg Category Ratio 10 Scale to measure perceived effort of the RST exercise equal to 70% MEP/MIP (Borg scale score of 7/10). The Borg Category Ratio Scale has been used in the limb literature and demonstrated accuracy in measuring %repetition max (RM). For example, a score of 2 is approximately 20% of a RM and a score of 7 is approximately 70% of a RM. To ensure patient privacy, telehealth sessions will take place in a private room using a UF secure telehealth platform (a secure version of Zoom). Attendance for weekly telehealth sessions will be tracked.

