In-Person Visit: CS patients will also have one in-person visit within participants’ homes or the research laboratory (DG-136) with a study team member at the mid-point of the RST program to ensure patients are using correct form and technique, to complete a safety and adverse event check, to answer any questions patients may have, and to assist with adherence issues. EMST/IMST devices will also be recalibrated by retesting MEP and MIP and setting the devices to 70%. LCADL ratings and functional speech measures (bamboo passage) will also be obtained.

Training Logs: CS patients will fill out daily training logs to track RST repetitions (adherence) and to note any adverse events related to RST. The PI will calculate the total number of repetitions completed by each participant at the conclusion of the training period.

Aim 1 Outcomes will include patient adherence to RST, attendance at telehealth/in-person treatment sessions, and adverse events associated with RST. We hypothesize that RST will be safe, well-tolerated, and feasible in CS patients as measured by high adherence to RST, attendance at all telehealth/in-person sessions, and no reported adverse events.

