- A Fiberoptic Endoscopic Evaluation of Swallowing (FEES) can result in discomfort, gagging or vomiting. Although extremely rare other complications that have been reported can include vasovagal episode (0.06%

reported incidence), laryngospasms (0.03% reported incidence), or epistaxis (0.3% reported incidence). The reported incidences of these adverse reactions to FEES are based on published reports in 6,000 patients.

- b) Aspiration (material in trachea) is always a possible risk during the FEES exam, as the test is intended to detect aspiration during swallowing.
- c) There are no documented complications of voluntary cough spirometry or pulmonary function testing.
- d) While RST has been safe and well-tolerated in a variety of patient populations, there is a chance it could result in dizziness, lightheadedness, fatigue, or shortness of breath.

**Potential Benefits:** Subjects may potentially benefit from participation through improved breathing, cough, and/or swallowing function. Participating in this study will also include an instrumental swallowing evaluation following surgery and may lead to the early identification of any swallowing impairments to minimize adverse effects of swallowing difficulty and to initiate preventative measures for risk of choking, respiratory difficulty and/or pneumonia post-operatively. Additionally, study participation may lead to sooner oral intake of food, liquids, and medications while in the hospital as a result of comprehensive swallowing testing being performed post-extubation.

**Conflict of Interest:** There is no conflict of interest to disclose for any study team member that is specifically relevant to this study.

**Summary and Conclusions:** This pilot study represents the first examination of the feasibility, safety, and physiologic impact of a targeted preoperative RST program in a small group of high-risk CS patients to prevent postoperative dysphagia and associated adverse outcomes. By carefully examining detailed aspects of physiology and health-related outcomes in a feasible design for this grant mechanism, the PI will collect high quality data to support her K99-R00 NIH grant application. These preliminary data will further inform future intervention paradigms in this challenging patient population where there is no current standard of care or evidence guided intervention guidelines for either pre or postoperative dysphagia management.

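### Dizziness, lightheadedness and fatigue, which the protocol names as possible training harms, have no pre-training record, and breathlessness has only a partial one that is not linked to the Aim 1 adverse events

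*Combined protocol and SAP*

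**What the plan says.** The study is a "longitudinal pilot cohort study" (Design), and "Twenty-five individuals undergoing cardiovascular surgery will be enrolled in this pilot project" (Participants). The sample size justification gives safety and feasibility as its main purpose.

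- **Expected harms.** Potential Risks says of RST that "there is a chance it could result in dizziness, lightheadedness, fatigue, or shortness of breath".
- **Before training.** The Research Evaluations paragraph states: "Before commencing the RST program, an initial research examination (pulmonary function testing, functional speech/dyspnea measures) will be completed". The dyspnea measure is the LCADL, a "15-item questionnaire that measures dyspnea during activities of daily living" (Functional Dyspnea Measure). No item on dizziness, lightheadedness or fatigue is described. The chart-history list under Health-related outcomes is open-ended and names none of the three.
- **During training.** The purposes of the telehealth sessions, held one to five times a week, include "to complete a safety and adverse event check". The mid-point visit has the same purpose, and there "LCADL ratings and functional speech measures (bamboo passage) will also be obtained". Patients also keep a daily log, in which they note events that they relate to RST.
- **After training.** The LCADL is completed again at Research Evaluation 2. Its before-and-after comparison belongs to Aim 2 (Aim 2 Outcomes, Statistical analyses, Table 9).
- **The safety outcome.** Aim 1 Outcomes lists "adverse events associated with RST. We hypothesize that RST will be safe, well-tolerated, and feasible in CS patients", and the hypothesis goes on to expect that none will be reported. The analysis is counts and percentages (Statistical analyses, Table 9). No rule is given for relatedness, for grading, or for what makes an event new or worse.

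**The concern.** The listed symptoms are ones that a patient waiting for heart surgery may already have. That is an assumption, since the documents give no prevalence, but the eligibility criteria do not exclude such patients. The plan itself hypothesises that dyspnea will improve with training, which presumes that some participants start out breathless.

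A single-arm study has two ways to judge whether a symptom belongs to the intervention: comparison with the patient's own earlier state, or someone's opinion. For three of the four named symptoms the first is not available, and for the fourth it exists but is not used in the safety analysis. The Aim 1 figure then depends on how symptoms are attributed, and the error can go either way. Counting long-standing symptoms makes training look worse than it is. Setting real training effects aside as cardiac makes it look better.

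Training starts directly after Research Evaluation 1 (RST Program), so a baseline not recorded then cannot be recovered reliably later.

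**Working it through.** The plan states no expected event rate, safety threshold or power, so there is no figure of its own to reproduce. The check has two parts.

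**1. Which symptom has what record**

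| Symptom named in Potential Risks | Before RST | During RST | Used with Aim 1 events? |
|---|---|---|---|
| Dizziness | none described | logs and safety checks | no baseline to use |
| Lightheadedness | none described | logs and safety checks | no baseline to use |
| Fatigue | none described | logs and safety checks | no baseline to use |
| Shortness of breath | LCADL (daily activities) | LCADL at mid-point, logs and safety checks | no link described |

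The LCADL is a partial baseline for the last row, because it concerns daily activities and not the repetitions themselves.

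**2. How far background symptoms could move the count**

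Inputs: n = 25 (Participants). Let b be the share of patients who have at least one of the symptoms regardless of RST; it is not in the documents, and the range 10% to 40% is assumed. The worst case takes every such patient as a reported event and RST as having no effect.

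- Expected number reporting = 25 × b
- Chance that nobody reports = (1 − b)^25

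| Assumed b | Expected of 25 | Chance of no report | Chance of at least one |
|---|---|---|---|
| 10% | 2.5 | 0.90^25 = 0.072 | 93% |
| 20% | 5 | 0.80^25 = 0.0038 | 99.6% |
| 40% | 10 | 0.60^25 = 0.0000028 | >99.99% |

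Now suppose that RST causes a symptom in an assumed r = 10% of those who had none. The crude share is b + (1 − b)r, and the new share is (1 − b)r.

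- b = 10%: crude 0.10 + 0.90 × 0.10 = 0.19, or 4.75 of 25; new 0.09, or 2.25 of 25.
- b = 20%: crude 0.20 + 0.80 × 0.10 = 0.28, or 7 of 25; new 0.08, or 2 of 25.
- b = 40%: crude 0.40 + 0.60 × 0.10 = 0.46, or 11.5 of 25; new 0.06, or 1.5 of 25.

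Over this range the crude count more than doubles while the number of new cases falls slightly. Without a baseline the two cannot be separated by rule.

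A count of zero still carries information. The exact one-sided 95% upper limit for 0 of 25 is 1 − 0.05^(1/25) = 11.3%, and the two-sided limit is 1 − 0.025^(1/25) = 13.7%. These limits apply to events as counted, after any attribution.

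**The case against.** A reader might infer that no symptom is recorded before training and that the safety rate is therefore uninterpretable. The documents support neither step. Breathlessness is measured with the LCADL before, midway through and after training. The outcome is restricted to events tied to RST, so an unchanged chronic symptom need not count. A research speech-language pathologist checks safety at least weekly, the investigator and team review events weekly, and there is medical oversight (Data Safety Monitoring Plan). Events other than these symptoms are unaffected, and a low count still limits the plausible risk.

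The calculation is also a worst case: b is assumed, and treating every background symptom as an event sets the relatedness wording aside. The expectation of no events is a descriptive hypothesis, not a go/no-go threshold.

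Finally, a baseline does not prove cause. Symptoms can progress or fluctuate before surgery, and the Design section explains why a single cohort was chosen. A summary confined to worsening would also miss an effect in someone already at the top grade, and a weekly grade may miss brief dizziness during a repetition.

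All of this stands, and it limits the size of the point. It does not remove it. The relatedness restriction and the weekly review are where the attribution is made, and for three of the four named symptoms those making it have no recorded earlier state to consult. Frequent checking after the start cannot supply that.

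**Conclusion.** The point holds for a limited set of symptoms. Dizziness, lightheadedness and fatigue have no described pre-training record. Breathlessness has a partial one that is not connected to the safety outcome. For these four symptoms, the Aim 1 count of RST-associated events is hard to interpret in a single-arm cohort awaiting cardiac surgery. The rest of the safety summary is not affected.

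The worst-case size is 2.5 to 10 of 25 patients reporting an event with no RST effect. It rests on an assumed background prevalence of 10% to 40% and on every symptom being reported as an event. The true effect would be smaller to the extent that unchanged symptoms are recognised and left out, but the plan gives no rule for doing so. The sample size does not change. This is a cheap improvement to a main aim, not a flaw that invalidates the pilot.

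**What to change.** 1. At Research Evaluation 1, before the first repetition, record a short checklist of the four symptoms in Potential Risks, each graded none, mild, moderate or severe.
2. Repeat the same items once a week at a telehealth safety check, and at the mid-point visit.
3. In the Aim 1 analysis, report baseline prevalence beside on-training prevalence, and the number of patients whose symptom is new or at least one grade worse than their own baseline.
4. Present this alongside the full list of all events, including transient symptoms during repetitions, and not in its place. The full list covers patients already at the highest grade and brief symptoms that a weekly grade would miss.
5. State that, without a control group, the comparison separates pre-existing from new or worse symptoms and does not establish that RST caused them.

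The cost is one short REDCap form at visits already planned, one or two minutes of participant time per visit, and a few sentences in the Aim 1 analysis.
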